Patients will be followed from the time of IUD insertion until the first occurrence of any of the following: uterine perforation, IUD expulsion, IUD removal, indication of IUD reinsertion, indication of new pregnancy, hysterectomy, death, expiration of IUD, disenrollment from the database, or end of the study period. All person-time at risk that meets these criteria will be included, and there will be no requirement for minimum or maximum follow-up time. All IUD insertions occurring with at least 12 months of enrollment before the insertion that are noted within the data sources will be included in the study. The index date will be captured for each insertion, and baseline data will be collected for each index date (Figure 2). The main analyses for the study will

assess only the first observed IUD insertion for each woman in the database. Secondary analyses will be conducted assessing subsequent insertions (i.e., not the first IUD insertion), as recorded in the database. The sequential number of each insertion, as captured in the data for each woman, will be collected and included as a baseline covariate within these secondary analyses.

Figure 2. Covariate data collection around index date

Exposures of postpartum status (based on pregnancy delivery date), breastfeeding status, IUD type, and menorrhagia (as a proxy for indication of use) will be assessed as of the index date of IUD insertion. Outcomes of uterine perforation and IUD expulsion will be assessed beginning on the index date. Baseline data—such as patient demographics, patient characteristics (e.g., personal history of gynecologic conditions such as endometriosis), procedure characteristics, medications, and comorbid conditions (e.g., diabetes)—will be collected from all time in the database before the index date (which will be defined as the day of IUD insertion) and on the index date (Figure 2). Provider characteristics, procedure-related characteristics, and indicators of a difficult insertion will be assessed on the index date (i.e., on the same date or within the same encounter as the index date). The variables to be obtained from each research site are provided in Sections 3.1 through 3.8.

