3.5 Indicators of a Difficult IUD Insertion

- *Cervical dilation*: indicator variable (0 = No, 1 = Yes) for whether cervical dilation was used during the IUD insertion procedure
- *Ultrasound guidance*: indicator variable (0 = No, 1 = Yes) for use of ultrasound guidance during placement of the IUD on the day of the IUD insertion
- *Paracervical block*: indicator variable (0 = No, 1 = Yes) for whether the patient received a paracervical block during the IUD insertion procedure
- *Provider note indicating a difficult insertion or complicated procedure*: indicator variable (0 = No, 1 = Yes) for whether the patient record includes a notation from the provider regarding a difficult insertion or complicated procedure
- *Use of misoprostol*: indicator variable (0 = No, 1 = Yes) for whether the patient received misoprostol during the 7 days before or on the date of the IUD insertion procedure

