for inclusion in propensity score models based on association with the study outcome (Brookhart et al., 2006); thus, analysts will not be blinded to the outcome. Baseline covariates to be considered for inclusion are listed in Sections 3 and 4.6. Categorical variables will be assessed for inclusion based on indicator coding of the categories. Continuous variables (including integer count variables) will be assessed for inclusion as continuous, dichotomous, and categorical (i.e., indicator coded) variables, as appropriate. Covariates will be included in the propensity score model if the crude hazard ratio is greater than 1.11 or less than 0.90. Additional confounders will be selected for inclusion within propensity score models if at least a 10% change in the hazard ratio of the exposure-outcome relationship occurs when adjusting for that variable, including at least a 10% change in any level of a categorical exposure variable relative to the referent group (> 52 weeks postpartum for postpartum period).

From the fitted logistic regression models, propensity scores and the overlap weights (Li et al., 2018) will be estimated for each IUD insertion. Overlap weighting is a relatively new weighting scheme to adjust for confounding effects. Overlap weights belong to a class of balancing weights, including commonly used weights for inverse probability weighting. Li et al. (2018) mathematically proved and verified in simulations that the overlap weights minimize asymptotic variance among balancing weights. Other advantages of overlap weights over inverse probability weighting include perfect balance for means and bounded weights avoiding explosive weights or the need for arbitrary truncation. In addition, the overlap weights focus on the naturally comparable “overlap” population, and therefore propensity score ‘trimming’ for a common support area is not necessary. The overlap weights have been applied in observational studies, for example, Schneider et al. (2001), although the term “overlap weights” was not established at that time.

For dichotomous exposure variables, the propensity score is the probability of being exposed. The propensity score for patient (insertion) i is denoted as $e_i = \Pr(Z_i = 1|X_i)$, where Z_i denotes the exposure (1= exposed, 0 = unexposed), and X_i denotes a vector of baseline covariates. The overlap weight for patient i is defined as follows:

$$w_i = \begin{cases} 1 - e_i, & Z_i = 1 \\ e_i, & Z_i = 0 \end{cases}$$

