Separate propensity score models will be developed for exposure-outcome pairings related to breastfeeding status, postpartum period, IUD type, and menorrhagia for uterine perforation and IUD expulsion. The list of propensity score models is provided in Section 9.3. Sections 6.2 and 6.3 includes additional information for specific objectives. In general, the selection of covariates for inclusion in propensity score models will be conducted only using first insertions. The association between baseline covariates and outcomes (crude hazard ratio) will be assessed only using the complete study population, which includes only the first IUD insertion for each woman. No covariate selection will be conducted for *subsequent* insertion models. Instead, for each specific pairing, covariates and terms included in the final propensity score model for first insertions will be included in the propensity score model for subsequent insertions. Additionally, IUD insertion count (the sequential number) may be included in the propensity score model if it is not balanced across exposure groups for *subsequent* insertions. Propensity scores and weights will be estimated from the corresponding propensity score models.

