4.6 Definition of Derived Variables and Subgroups

The variables described in Table 1 will be derived by RTI-HS using the data provided by the four research sites. Since the unit of observation in the data provided by the research partners will be an IUD insertion, these variables will be calculated for each insertion and included in the final dataset. If a woman has more than one eligible insertion in the dataset, the variables will be derived for each insertion using data relevant to that insertion.

Table 1. Definition of Derived Variables

Variable	Definition ^a
Baseline covariates	
IUD insertion count	The number of eligible IUD insertions for the woman as of the index date (including the index insertion). IUD insertion count increases by 1 each time a new index date is identified for the woman
Initial IUD insertion	Indicator variable: If IUD insertion count = 1 then initial IUD insertion = 1 If IUD insertion count > 1 then initial IUD insertion = 0
Difficult insertion	Indicator variable: 1 = Yes if any of the following occur on the index date (or in 7 days before index date for misoprostol): cervical dilation, ultrasound guidance, paracervical block, provider note, use of misoprostol 0 = No if none of the above indicators of difficult insertion are found on the index date
Age tertile	Categorical variable for age based on tertiles (or closest integer cut point [i.e., in years]) for all ages at all first index dates observed within the data
Duration of look-back period	Derived number of days, starting on the date of start of enrollment or first clinical encounter in the EHR database and ending on the index date Duration of look-back period is calculated for each index date
Categorical indicator for provider number of insertions in previous year	Indicator variable: 0 = fewer than 50 provider number of IUD insertions in the 365 days prior to and on the index date, 1 = 50 or more provider number of IUD insertions in the 365 days prior to and on the index date
Provider annualized number of insertions in previous year	Provider number of IUD insertions in previous year divided by provider length of employment in previous year , multiplied by 365

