6.3.2 Analysis of Difficult Insertion

The prevalence of indicators of a difficult insertion (objective 13) will be presented via contingency tables including frequencies and percentages of each level of each exposure and outcome variable for five individual indicators of difficult IUD insertion—cervical dilation, ultrasound guidance, paracervical block, provider note, use of misoprostol—plus an indicator for *any* difficult insertion. Analyses will be conducted for the first observed IUD insertion using the pooled data and by data source (Analysis Tables 13.1-13.5). In addition, difficult insertion indicators will be included in summary tables of baseline characteristics.

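### The crude hazard ratio rule can select the index-date provider note, possibly a result of perforation, into the propensity scores, and no planned analysis must give the adjusted primary hazard ratio without it

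*SAP*

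**What the plan says.** The pool of candidates is set in SAP 4.1.5: "Baseline covariates to be considered for inclusion are listed in Sections 3 and 4.6". The entry rule in the same section is "Covariates will be included in the propensity score model if the crude hazard ratio is greater than 1.11 or less than 0.90"; a second route is a change of at least 10% in the exposure hazard ratio. For the first route, "The association between baseline covariates and outcomes (crude hazard ratio) will be assessed only using the complete study population".

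SAP 3.5 lists, among the indicators of a difficult insertion, "Provider note indicating a difficult insertion or complicated procedure". SAP 4.6, Table 1, places the composite variable for a difficult insertion, of which the note is one of five components, under baseline covariates. SAP 6.3.2 adds that "difficult insertion indicators will be included in summary tables of baseline characteristics". Protocol 9.3.1 holds the same indicators, and Protocol 9.7.1.3.2 makes every baseline variable of 9.3.1 a candidate.

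On timing, SAP Section 3 (Study Design) says that "indicators of a difficult insertion will be assessed on the index date" and, in the same paragraph, "Outcomes of uterine perforation and IUD expulsion will be assessed beginning on the index date".

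The only other confounder-adjusted analysis of the primary objectives is the unweighted Cox model of SAP 6.2.1 (Tables 1.4 and 2.4). Its covariates are also chosen by association with the outcome.

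**The concern.** A propensity score should balance what was settled before exposure could affect the outcome. The note is written after both primary exposures are fixed, and nothing restricts it to difficulty that came before a perforation. A clinician who recognizes a perforation during insertion has every reason to record a complicated procedure. Such a note is caused by the outcome, so its crude hazard ratio is raised and the entry rule favors it.

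Once selected, the overlap weights balance the note between exposure groups. To the extent that the note results from perforation, the primary hazard ratio is then partly conditioned on its own outcome. The same scores feed the adjusted rate ratios and differences, and models 10-15 for subsequent insertions inherit the chosen covariates (SAP 9.3).

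**Working it through.** **Inputs from the documents.** Perforation risk is 1.3 per 1,000. Expected first insertions are 225,000, of which 60,000 have breastfeeding status, split 60:40. The postpartum split is 5:20:5:70 (Protocol 9.5). Weights are those of SAP 4.1.5.

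**Assumed inputs, not in the documents.** b is the background note frequency, by group where it differs. q is the share of perforations that trigger a note. The note has no effect of its own on perforation, it is the only covariate in the score, and the risk ratio stands in for the hazard ratio because the event is rare.

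**Plan's own figure.** Objective 1 has 60,000 x 0.0013 = 78 events. Schoenfeld power at a hazard ratio of 2.0 and 60:40 is 85.1%, against 85% in Protocol Table 4. For ≤ 6 weeks (168,750 insertions, 5:70) it is 72.6%, against 73%.

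**Step 1: would the rule admit the note?** The screen has 225,000 x 0.0013 ≈ 292 events. Let f = Pr(note | perforation) = b + (1-b)q. The crude ratio is [f/(1-f)] x [(1-b)/b].
- b = 10%, q = 5%: f = 0.145, ratio 1.53.
- b = 2%, q = 20%: f = 0.216, ratio 13.5.
- To exceed 1.11 in expectation, q must be 0.22% at b = 2%, 0.55% at b = 5%, or 1.09% at b = 10%. That is 0.6, 1.6 or 3.2 of the 292 events.
- Exact binomial probability of entry for b = 2-10%: 96% or more at q = 5-20%, 70-97% at q = 2%, and 56-84% at q = 0, where chance alone is at work.

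**Step 2: one case for objective 1 in full.** True ratio 2.0, notes 10% in exposed and 5% in referent women, q = 20%.
- Risks: p0 = 0.0013/(0.6 x 2 + 0.4) = 0.0008125; p1 = 0.001625.
- Note given perforation: 0.10 + 0.90 x 0.20 = 0.28 exposed; 0.05 + 0.95 x 0.20 = 0.24 referent.
- Note overall: 0.10029 exposed, 0.05015 referent.
- Propensity: with note, 0.6 x 0.10029/(0.6 x 0.10029 + 0.4 x 0.05015) = 0.7500; without note, 0.5869.
- Weighted risk, exposed (weight 1-e): 0.001625 x (0.28 x 0.2500 + 0.72 x 0.4131)/(0.10029 x 0.2500 + 0.89971 x 0.4131) = 0.001505.
- Weighted risk, referent (weight e): 0.0008125 x (0.24 x 0.7500 + 0.76 x 0.5869)/(0.05015 x 0.7500 + 0.94985 x 0.5869) = 0.000855.
- Ratio: 1.76, against a true 2.0.

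**Step 3: range for objective 1, true ratio 2.0.**

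| Notes, exposed vs referent | q = 5% | q = 20% | q = 50% |
|---|---|---|---|
| 2% to 10%, equal | 2.00 | 2.00 | 1.98-2.00 |
| 0.1%, equal | 2.00 | 1.95 | 1.77 |
| 6% vs 5% | 1.98 | 1.93 | not used |
| 10% vs 5% | 1.94 | 1.76 | not used |
| 5% vs 10% | 2.07 | 2.30 | not used |

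At 10% vs 5%, power falls from 85% to 82-69%. With a true ratio of 1.0, the same q range gives 0.97-0.88 at 10% vs 5% and 1.04-1.15 at 5% vs 10%.

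**Step 4: objective 2, all three early categories at 2.0, q = 5-20%.** Equal notes of 2-5% give 2.00. Notes of 10% in the early categories vs 5% in the referent give 1.91-1.67; 5% vs 10% gives 2.05-2.22.

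**Scale.** In objective 1, SE(ln HR) = 1/√(78 x 0.24) = 0.231. The values 1.76 and 2.30 lie about 0.6 SE from 2.0.

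**The case against.** The strongest reply is that the planned outputs already reveal most of this. Table Layout 9 tabulates the note by breastfeeding status, by postpartum category and by perforation, which informs the frequencies assumed above. Table Layout 5 gives the exposure hazard ratio adjusted for each candidate alone and states whether it entered the score. In the worked case, one-covariate regression gives 1.775 and overlap weighting 1.761, so a material shift would be visible. This stands. It would be wrong to infer that a report following the plan would hide the problem. What remains missing is the adjusted primary hazard ratio with all other covariates in and the note out. The Cox sensitivity model might omit the note but need not. The sparse-cell rule in SAP Section 6 permits exclusion without requiring it.

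Second, the note may record real difficulty that came before any perforation, in which case leaving it out costs confounding control. With no triggering, an assumed risk ratio of 2-3 for the note, and notes at 10% vs 5%, omission moves 2.0 to 2.0 x 1.10/1.05 = 2.10 or 2.0 x 1.20/1.10 = 2.18. At 5% vs 10% it gives 1.91-1.83. This is comparable in size to the harm from inclusion, and the fix must allow for it.

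Third, Protocol 9.9 acknowledges a lag between perforation and care-seeking, so few perforations may be recognized at insertion. Protocol 4.6.3 describes baseline as pre-insertion and mentions insertion difficulty separately. Both temper the concern; neither removes the note from the pool.

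**Conclusion.** The gap is real and modest: a variable recorded after exposure, which the outcome may cause, can be selected into the weights because of its association with that outcome. Entry is probable under the assumed inputs but depends on the data.

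A reader might infer that the primary hazard ratios will be biased, or biased toward 1. The documents do not support that, because they give neither the note's frequency nor the share of perforations recognized at insertion. Bias is negligible with notes of 2% or more and equal between groups. It becomes material only when notes are rare and largely triggered by perforation, or clearly unequal between groups, and in the unequal case it can go either way. Other covariates in the score may absorb part of an imbalance.

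Nor does the point extend to cervical dilation, ultrasound guidance, paracervical block, misoprostol or the concomitant procedures. These may be mediators or proxies for pre-insertion factors, and Protocol Section 7 itself treats dilation as a potential confounder. Their inclusion is debatable and not shown to be an error.

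The change is cheap and best made before covariate selection, since the analysts who select will see the outcomes.

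**What to change.** State in SAP 4.1.5 that the provider note, and any composite containing it, is not a candidate for propensity score models 1-9 (and so not for 10-15 by inheritance) or for the regression sensitivity models in Tables 1.4 and 2.4. Add one prespecified overlap-weighted sensitivity analysis for objectives 1 and 2 that puts the note back, so that the multivariable-adjusted hazard ratio is reported with and without it. Keep all indicators for objective 13. Leaving out other index-date indicators is optional.

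The cost is a short change of wording and one extra weighted analysis on data already held. The price in the main model is any pre-insertion risk information that the note carries; the added analysis would show how far the estimate depends on it. The comparison cannot by itself say whether a difference is removed bias or lost confounding control, so it should be read beside Layout 9.

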- **Continuous enrollment**, in days, that each individual is in the data source will be calculated starting on the earliest date of date of enrollment in database or date of first clinical encounter in database and ending on the earliest of date of disenrollment from database, date of last clinical encounter in database, or end date of study period, allowing up to one 31-day gap in enrollment each year to be considered continuously enrolled. The individual's start and end dates in the enrollment files will be used for KPNC, KPSC, and KPWA. For RI, the start date will be designated as the patient's first clinical encounter within the dataset, and the end date will be the patient's last observation within the dataset. There may be multiple continuous enrollment periods for a woman who moves out of then back into the database.
- **Live birth at most recent delivery:** indicator variable (0 = No, 1 = Yes) for whether the patient had pregnancy ending in live birth within the past 52 weeks.

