9	Interaction of breastfeeding and early vs. late postpartum (breastfeeding/ \leq 14 weeks; breastfeeding/ $>$ 14 weeks; no breastfeeding/ \leq 14 weeks; no breastfeeding/ $>$ 14 weeks [referent])	Uterine perforation

^a Secondary objectives include dichotomization of “early” and “late” postpartum categories. Separate propensity score models will not be *developed* for these objectives. Rather, the propensity scores calculated with the four-category variable will be used, and the distribution of scores will be collapsed into the categories for each secondary objective. Assessment of distributions of propensity scores will be performed within these collapsed categories.

Propensity scores for dichotomous exposure variables will be estimated by fitting a logistic regression model that incorporates data source (i.e., KPNC, KPSC, KPWA, or RI) and measured potential predictors of exposure as independent variables (all baseline variables in Section 9.3.1 will be considered). The dependent variable in the propensity score model is exposure status (e.g., women breastfeeding at the time of IUD insertion vs. not breastfeeding at the time of IUD insertion).

Propensity scores for the categorical variable (i.e., timing of postpartum insertion) will be estimated by fitting a multinomial logistic regression model that incorporates data source (i.e., KPNC, KPSC, KPWA, or RI) and measured potential predictors of exposure as independent variables (all baseline variables in Section 9.3.1 will be considered). The dependent variable in the propensity score model is exposure category (i.e., ≤ 6 weeks postpartum; > 6 and ≤ 14 weeks postpartum; > 14 and ≤ 52 weeks postpartum; > 52 weeks postpartum [referent]).

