3.3 Baseline Demographic and Clinical Characteristics

- *Age*: age in years as of the index date
- *Race/ethnicity*: categorical variable with nine categories: non-Hispanic white, Hispanic white, non-Hispanic black, Hispanic black, other Hispanic, Asian/Pacific Islander, multiple races/ethnicities, other race/ethnicity, unknown
- *Smoking status*: indicator variable for smoking status as of the index date (0 = no recent smoking, 1 = recent smoking [active smoker within 365 days prior to or on the index date])
- *Body mass index (BMI)*: continuous variable assessed at the index date or the closest date before or after the index date
- *Dysmenorrhea*: four-level categorical variable for whether the patient was diagnosed with dysmenorrhea
 - Diagnosed in the year prior to or on the index date, but not diagnosed before that time
 - Not diagnosed in the year prior to or on the index date, but was diagnosed before that time
 - Diagnosis recorded within year prior to or on the index date and also before that time
 - No diagnosis of dysmenorrhea within the data
- *Fibroids*: indicator variable (0 = No, 1 = Yes) for whether the patient was ever diagnosed with or reported diagnosis of uterine fibroids prior to or on the index date
- *Parity*: cumulative number of viable pregnancies (i.e., carried to at least 20 weeks gestation) prior to and on the index date
- *Cesarean delivery* will be captured only among women who had at least one delivery prior to the index date and will be captured in two variables:
 - Indicator variable (0 = No, 1 = Yes) for whether the patient *ever had a Cesarean delivery* prior to or on the index date
 - Indicator variable (0 = No, 1 = Yes) for whether the patient had a *Cesarean delivery for the most recent delivery* that is within 52 weeks prior to or on the index date
- *Calendar year of index date*: calendar year of the index date (2001-2018, depending on data source)
- *Month of index date*: calendar month of the index date (1-12 corresponding to January-December, respectively).

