3.8 Other Parameters

- *Database*: categorical variable of the four data sources included in the study
- *Live birth at most recent delivery*: indicator variable (0 = No, 1 = Yes) for whether the patient had a pregnancy ending in live birth within the 52 weeks before the index date
- *Date of start of most recent (continuous) enrollment* (KPNC, KPSC, and KPWA only) is the date, prior to the index date, on which the woman started enrollment in an eligible insurance plan (one gap of ≤ 31 days per year will be allowed)

4 General Statistical Considerations

All issues concerning patient eligibility, data consistency checks, permissible data modifications, and coding of medical terms and medication will be documented and maintained by research partners following the Data Structure Template (a central document including operational definitions developed by RTI Health Solutions (RTI-HS) and the data source research partners) and the Work Practice Document for quality control. All statistical issues including derived variables are to be detailed in this statistical analysis plan. Determination of sample size was detailed in the study protocol.

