> 52 weeks or no delivery	xx (x.x)	xx (x.x)	xx (x.x)	xx (x.x)	xx (x.x)	xx (x.x)	xx (x.x)
≤ 14 weeks	xx (x.x)	xx (x.x)	xx (x.x)	xx (x.x)	xx (x.x)	xx (x.x)	xx (x.x)
> 14 weeks or no delivery	xx (x.x)	xx (x.x)	xx (x.x)	xx (x.x)	xx (x.x)	xx (x.x)	xx (x.x)
≤ 36 weeks	xx (x.x)	xx (x.x)	xx (x.x)	xx (x.x)	xx (x.x)	xx (x.x)	xx (x.x)
> 36 weeks or no delivery	xx (x.x)	xx (x.x)	xx (x.x)	xx (x.x)	xx (x.x)	xx (x.x)	xx (x.x)
IUD type							
LNG-IUD	xx (x.x)	xx (x.x)	xx (x.x)	xx (x.x)	xx (x.x)	xx (x.x)	xx (x.x)
Copper IUD	xx (x.x)	xx (x.x)	xx (x.x)	xx (x.x)	xx (x.x)	xx (x.x)	xx (x.x)
Unknown	xx (x.x)	xx (x.x)	xx (x.x)	xx (x.x)	xx (x.x)	xx (x.x)	xx (x.x)

Characteristic	Overall	Uterine Perforation			IUD Expulsion		
	(N = XXX,XXX)	Yes (N = XX,XXX)	No (N = XX,XXX)	Undetermined (N = XX,XXX)	Yes (N = XX,XXX)	No (N = XX,XXX)	Undetermined (N = XX,XXX)
Menorrhagia in the past year	xx (x.x)	xx (x.x)	xx (x.x)	xx (x.x)	xx (x.x)	xx (x.x)	xx (x.x)
Diagnosis recorded only within 1 year	xx (x.x)	xx (x.x)	xx (x.x)	xx (x.x)	xx (x.x)	xx (x.x)	xx (x.x)
Diagnosis recorded only before 1 year	xx (x.x)	xx (x.x)	xx (x.x)	xx (x.x)	xx (x.x)	xx (x.x)	xx (x.x)
Diagnosis recorded both within and before 1 year	xx (x.x)	xx (x.x)	xx (x.x)	xx (x.x)	xx (x.x)	xx (x.x)	xx (x.x)
No diagnosis	xx (x.x)	xx (x.x)	xx (x.x)	xx (x.x)	xx (x.x)	xx (x.x)	xx (x.x)

BMI = body mass index; IUD = intrauterine device; LNG-IUD = levonorgestrel-releasing intrauterine system; Q1 = lower quartile (i.e., 25th percentile); Q3 = upper quartile (i.e., 75th percentile); SD = standard deviation.

^a Age categories were based on tertiles of the distribution.

^b Available only in the KPSC database.

^c Available in the KPSC database; partially available in the KPWA and RI databases.

^d Cesarean delivery summarized only among women who had at least one delivery before the index date.

^e Available in the KPNC, KPSC, and KPWA databases.

^f Continuous enrollment is not a baseline covariate. It is included only for summary purposes.

Generated using xxxx.sas on xxxxxxx.

Programming note 1: For tables of first insertions, N is number of patients. For tables of subsequent insertions, N is number of insertions.

Programming note 2: For variables with missing data, number of missing data will be reported.

Programming note 3: IUD insertion count will not be shown for tables using only first insertions because it will be 1 for every patient.

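### Recent cesarean can enter the four-category postpartum propensity models although it can never be Yes in the referent group; if it enters, women with a recent cesarean lose essentially all weight

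*SAP*

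**What the plan says.** SAP 4.1.5 defines the pool and the entry rule: "Baseline covariates to be considered for inclusion are listed in Sections 3 and 4.6", and "Covariates will be included in the propensity score model if the crude hazard ratio is greater than 1.11 or less than 0.90". The screen is run on first insertions in the complete study population. A second route in is a change of at least 10% in the exposure hazard ratio. No variable is barred by name from the postpartum-timing models. Models 11 and 14 (subsequent insertions) take over the terms of models 2 and 6 without a new selection (SAP 9.3).

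SAP 3.3 lists two cesarean indicators: ever, and at the most recent delivery "that is within 52 weeks prior to or on the index date". Both "will be captured only among women who had at least one delivery prior to the index date". The protocol also makes the recent-cesarean indicator a candidate: in its Section 9.7.1.3.2, "all baseline variables in Section 9.3.1 will be considered", and 9.3.1 contains it.

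The referent of the four-category exposure is insertion more than 52 weeks after delivery or with no recorded delivery in that period (SAP 4.6, Table 1). For K groups the SAP 4.1.5 weight is w_ik = 1/(e_ik Σ_j 1/e_ij). No trimming is done, and all insertions stay in.

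Recent live birth is placed differently. SAP 3.8, Other Parameters, defines it as "whether the patient had a pregnancy ending in live birth within the 52 weeks before the index date". The protocol has it in 9.3.4, outside the 9.3.1 pool.

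**The concern.** A recent cesarean presupposes a delivery within 52 weeks, so for this exposure the variable is partly a restatement of group membership and not a confounder of it. A propensity model containing it will fit a referent probability of about zero for every woman with a recent cesarean, and the overlap weight then discards her.

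The screen makes this more likely when timing matters: a crude hazard ratio for recent cesarean compares a wholly postpartum group with a mostly referent one. The stronger the true timing effect, the surer the admission.

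The planned checks would not catch it. Once these women carry no weight, recent cesarean is effectively 0 in every weighted group and the 0.20 standardized-difference limit is met trivially. The stated repair for imbalance adds model terms; it does not remove a covariate. At stake are who primary objective 2 describes and how precisely it is answered.

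**Working it through.** **Inputs.** From protocol 9.5: 225,000 first insertions; allocation 5:20:5:70, that is 11,250 / 45,000 / 11,250 / 157,500, so 67,500 postpartum women; perforation risk 1.3 per 1,000; breastfeeding status available for 60,000, split 60:40; two-sided alpha 0.05. Assumed, not in the documents: a cesarean share of 20-40% of recent deliveries (28% where one value is used), equal across the three postpartum groups, and coding as No throughout the referent.

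**1. Stated power.** Schoenfeld: power = Φ(|ln HR| √(d p₁p₂) − 1.96). For ≤ 6 weeks versus referent, d = 168,750 × 0.0013 = 219.4 and p₁p₂ = (5/75)(70/75) = 0.0622, so power = Φ(0.693 × 3.695 − 1.96) = Φ(0.60) = 72.6%. Table 4 gives 73%. Its 15 distinct cells all reproduce within one point.

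**2. Crude hazard ratio inherited by recent cesarean.** With postpartum hazard ratio H, cesarean share s and no effect of cesarean itself, the crude ratio is H divided by the mean hazard among No women, [0.70 + 0.30(1−s)H] / [0.70 + 0.30(1−s)]. At s = 0.28:
- H = 1.3: 1.3 / (0.9808/0.916) = 1.21
- H = 1.5: 1.5 / (1.024/0.916) = 1.34
- H = 2.0: 2.0 / (1.132/0.916) = 1.62

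All exceed 1.11.

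**3. Chance of passing the screen.** Use a normal approximation for the log hazard ratio with 225,000 × 0.0013 = 292.5 events. At s = 0.3 the Yes proportion is 0.30 × 0.3 = 0.09, so the standard error is 1/√(292.5 × 0.09 × 0.91) = 0.204. For s from 0.2 to 0.4, the chance is 94-99% at H = 2.0 and 83-88% at H = 1.5. With no effect at all, noise alone passes it 56-67% of the time, because the rule has no significance criterion.

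**4. Weight after entry.** When the referent probability e₀ goes to 0, Σ 1/e is dominated by 1/e₀, so w_k ≈ e₀/e_k, which also goes to 0. A multinomial fit on the 5:20:5:70 cells with s = 0.3 shows this: after 6 Newton steps women with a recent cesarean hold 0.19% of their group's weight, after 12 steps 0.0005%. Postpartum women without one keep weights of 0.43 / 0.11 / 0.43.

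**5. Power on the women who keep weight, hazard ratio 2.0.**

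| Cesarean share | Women losing weight | ≤ 6 wk | > 6 to ≤ 14 wk | > 14 to ≤ 52 wk |
|---|---|---|---|---|
| not entered | 0 | 72.6% | 99.7% | 72.6% |
| 20% | 13,500 | 63.5% | 99.0% | 63.5% |
| 30% | 20,250 | 58.1% | 98.2% | 58.1% |
| 40% | 27,000 | 52.0% | 96.7% | 52.0% |

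**6. Collapsed objectives.** The 14-week comparison sums category scores and uses the two-group weight 1 − e (SAP 6.2.2.2 and 4.1.5). A ≤ 14 week woman with a recent cesarean has a late-group probability of 5/30, so she keeps a weight of about 0.17. Within her covariate stratum she is compared only with later insertions inside 52 weeks. The > 36 week group likewise contains women with a recent delivery. This is distorted weighting, not removal.

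**7. The forced breastfeeding term.** SAP 4.1.5 puts breastfeeding into the same models, and SAP 3.1 codes it No in the referent. With Undetermined as its own level, 36,000 + (67,500 − 60,000) = 43,500 women lose weight and 24,000 keep it, giving power of about 34% / 85% / 34% with cesarean left out. With Undetermined merged into No, 31,500 keep weight and power is about 43% / 93% / 43%. Breastfeeding (Undetermined separate) and cesarean together give 23-29% / 66-78% / 23-29%.

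**The case against.** The strongest reply is that entry is conditional. If cesarean carries an effect of its own, say 0.7, then with H = 1.5 and s = 0.28 the crude ratio is 1.05/1.118 = 0.94 and the variable fails the crude screen. That stands, and is why entry is called likely and not certain.

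Safeguards exist. SAP 6 allows sparse cells (below 10) to be combined or excluded, overlap and weights are inspected, and the table layouts let the variable list be adjusted after data review. All are discretionary, and none requires a covariate that determines exposure to be removed. The crude hazard ratios and the unweighted covariate-adjusted sensitivity analysis of objective 2 are untouched by the weights, but they do not replace the weighted primary result.

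A reader might go further and infer that recent live birth also enters, which would empty the postpartum groups. At an assumed live-birth share of 98-99.5%, only 338-1,350 of 67,500 women would keep weight, with 0.07-0.3 expected events in each 5% group. The documents do not support treating this as planned. Live birth is a candidate only if all of Section 3 is the pool, yet Section 3 also holds outcomes and censoring dates. It sits under Other Parameters, and the protocol pool omits it. What remains is an ambiguity: the Table Layout 1 footnote "Continuous enrollment is not a baseline covariate. It is included only for summary purposes" covers only continuous enrollment, and nothing says the same of live birth.

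**Conclusion.** The point holds for recent cesarean. Both documents make it a candidate for the four-category postpartum models, it has a structural zero in the referent, and the crude screen favors its entry. If it enters, women with a recent cesarean are in effect removed from objectives 2, 23, 31 and 32 and from the four-category parts of 18 and 26. Taken alone, this costs the two 5% groups about 9 to 21 points of power at a hazard ratio of 2.0 and the > 6 to ≤ 14 week group at most about 3.

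Three stronger inferences are not supported. The indicator is not confined to recently delivered women: it is captured after any earlier delivery, and only the value Yes is so confined. The collapsed 14- and 36-week objectives do not lose all weight. And the fall from 73% to 52-64% is not the SAP's full position, since the forced breastfeeding term already takes the small groups to about 34-43%.

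The sizes rest on the assumed cesarean share, equal covariate shares across the postpartum groups, and power computed on retained women as an approximation to the weighted sandwich analysis.

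**What to change.** State in SAP 4.1.5, with a note in 9.3, that cesarean at the most recent delivery within 52 weeks is not a candidate in propensity models 2, 6, 11 and 14, and confirm that live birth within 52 weeks is not one either. Keep ever-cesarean and parity as candidates there. Keep recent cesarean in the breastfeeding models (1, 5, 9, 10 and 13), where every woman has a recent delivery.

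The cost is a sentence and a table note, with no new data or patients, made before the scores are fitted. Differences in recent cesarean among the three postpartum groups would then be controlled only through ever-cesarean and parity, but can still be tabulated.

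This is necessary but not sufficient. The breastfeeding term in the same models must be corrected at the same time, or the power in protocol Table 4 cannot be recovered.
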